Objective 1. Determine whether CBZ treatment reduces hepatic ATZ load in AT-deficient patients with severe liver disease.

The primary analysis will test for differences between the treated and placebo groups in the change from baseline to follow-up in the number of hepatocytes with PAS+/diastase-resistant globules using an unpaired t-test (or nonparametric equivalent if appropriate). Given the small sample size, we do not assume that randomization will balance treated and placebo groups at baseline with respect to outcome variables. Therefore, we will compare changes over the course of the treatment rather than differences at the end of the treatment. Secondary analyses will look at the area of a liver section occupied by these globules and the

A Preliminary Study of the Efficacy and Safety of Carbamazepine in Severe Liver Disease Due to Alpha-1 Antitrypsin Deficiency

steady state level of ATZ by immunoblot again using an unpaired t-test (or nonparametric equivalents if appropriate) of the differences between the treated and placebo groups in changes from baseline to follow-up.

Given that the sample is small, randomization may not balance the groups with respect to important covariates, though our ability to detect statistically significant differences is likewise limited to relatively large effect sizes. Furthermore, the number of variables that could be adjusted for in a regression model is also limited by the sample size, as is our ability to do subgroup analyses. However, as exploratory analyses, we will compare the distributions of important confounders between treated and placebo groups and fit multiple linear regression models that include independent variables, in addition to treatment group and baseline values of outcome measures, with variables whose distributions are markedly imbalanced between treatment groups.

Objective 2. Determine whether CBZ treatment reduces hepatic fibrosis in AT-deficient patients with severe liver disease.

Analysis will proceed as in objective 1; however, the outcome will be hepatic fibrosis. The primary analysis will compare treatment group differences in baseline to follow-up changes in hepatic hydroxyproline concentration using an unpaired t-test (or nonparametric equivalent if appropriate). Secondary outcome measures will include Sirius red staining of the liver. Exploratory analyses using multiple regression models will proceed as described above.

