Objective 3. Determine whether CBZ treatment reduces portal pressure in AT-deficient patients with severe liver disease as assessed by serial hepatic venous pressure gradient measurements.

Analysis will proceed as in objective 1; however, the outcome will be portal pressure. The analysis will compare treatment group differences in baseline to follow-up changes in hepatic wedge pressure gradient as the outcome. An unpaired t-test (or nonparametric equivalent if appropriate) will be the primary analysis and we will conduct exploratory multiple regression analyses to adjust for the possibility of covariate imbalances as described above.

In subjects with intrahepatic collateral vessels (visualized radiologically) together with HVPG less than 10 at baseline, we will assess the outcomes in all categories other than objective 3

It is possible that we will not see a difference in hepatic ATZ load or fibrosis because of variability and heterogeneity within the liver but that the drug will produce a stabilization or improvement in overall clinical status. Therefore, as an exploratory analysis we will assess whether CBZ treatment will lead to stabilization or improvement in disease severity as measured by the MELD score. The analysis will compare treatment group differences in baseline to follow-up changes.

Analysis will proceed as above; however, the outcome will be the MELD score. Unpaired t-tests (or nonparametric equivalent if appropriate) will be the primary analysis and we will conduct exploratory multiple regression analyses to adjust for the possibility of covariate imbalances.

A Preliminary Study of the Efficacy and Safety of Carbamazepine in Severe Liver Disease Due to Alpha-1 Antitrypsin Deficiency

Power calculations

Resources limited the sample size, so we performed power calculations with an effect size estimated from prior work on the primary outcome for this study – the number of hepatocytes with PAS+/diastase-resistant globules.

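### The exploratory regressions choose covariates by chance imbalance between arms, so the model cannot be fixed before unblinding and loses power against prespecified prognostic adjustment.

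*Combined protocol and SAP*

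**What the plan says.** Under Statistical considerations, Analysis, Objective 1, the primary test is an unadjusted two-group comparison of change from baseline. The regression is secondary to it and is introduced with "However, as exploratory analyses". It has two steps. First, "we will compare the distributions of important confounders between treated and placebo groups". Then linear models are fitted whose further terms, "in addition to treatment group and baseline values of outcome measures", are those "with variables whose distributions are markedly imbalanced between treatment groups". The same section concedes that "the number of variables that could be adjusted for in a regression model is also limited by the sample size", but sets no maximum, names no candidate and does not say how large an imbalance must be.

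Objective 2 (fibrosis) refers back to this method. Objective 3 (HVPG) says "we will conduct exploratory multiple regression analyses to adjust for the possibility of covariate imbalances as described above". The MELD paragraph repeats the idea.

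The Randomization section stratifies on ongoing non-selective beta-blocker treatment because that treatment may lower HVPG. The stratum is not listed as a regression term.

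**The concern.** Randomization makes any difference in covariate distributions a matter of chance. How large that difference is says nothing about how strongly the covariate predicts outcome, and prediction is what makes adjustment worthwhile. Three consequences follow.

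- The covariates that enter are those most correlated with treatment, which inflate the standard error of the treatment effect.
- A prognostic covariate that happens to be balanced is left out, and its gain in precision is lost. Stratification balances beta-blocker use by design, so the rule would normally pass over the one covariate that the protocol ties to an outcome.
- Imbalance can be judged only once the allocation is known, and the word markedly leaves room for judgement. The model therefore cannot be written down before unblinding.

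At stake is the usefulness of the adjusted estimates in a 30-patient trial whose own plan expects randomization may leave important covariates unbalanced.

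**Working it through.** **1. The plan's own figure.** From Power calculations: 20 treated, 10 controls, two-sided 5%, standardized effect 1.1, 80% power. The standard error is √(1/20 + 1/10) = 0.387 SD, and 1.1/0.387 = 2.84. The normal approximation gives Φ(2.84 − 1.96) = 81.1%; the exact noncentral t with 28 df gives 78.3%. The stated 80% is reproduced. It refers to the unadjusted t-test. The plan gives no power figure for the regression.

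**2. How often chance triggers the rule.** The documents give no threshold. Taking an absolute standardized difference d above 0.5 as marked, the chance per covariate is 2 × [1 − Φ(0.5 × √(20 × 10/30))] = 2 × [1 − Φ(1.29)] = 0.197, about one in five.

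**3. Cost of a selected covariate with no prognostic value.** The variance of the treatment effect is multiplied by about 1 + (2/3)(1/3)d². This is 1.06, 1.14 and 1.22 for d = 0.5, 0.8 and 1.0.

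**4. Simulation with the baseline outcome always in the model.** Allocation 20:10; effect 0 or 1.1 SD of change; 20,000 trials per setting. Assumed inputs, none given in the documents: baseline/follow-up correlation 0.5 or 0.8; 1 or 4 candidates; candidates jointly explaining 0%, 30% or 50% of residual variance; marked imbalance taken as p<0.05 or d>0.5. The table shows correlation 0.8 with d>0.5. Prespecified means all candidates are always included.

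| Candidates, variance explained | t-test power | Baseline-only power | Rule power | Prespecified power | Rule type I error |
|---|---|---|---|---|---|
| 1, 30% | 78.3% | 81.2% | 84.2% | 91.5% | 3.8% |
| 1, 50% | 78.2% | 80.7% | 86.1% | 97.2% | 2.7% |
| 4, 30% | 78.2% | 81.1% | 80.8% | 87.1% | 3.6% |
| 4, 50% | 78.4% | 81.1% | 83.9% | 95.3% | 2.7% |
| 4, 0% | 77.8% | 80.3% | 76.0% | 73.0% | 5.0% |

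Over all settings with prognostic candidates:
- power is 81–92% under the rule and 87–99% prespecified, a loss of about 5 to 16 points;
- type I error is 2.6–4.5% and interval coverage 95.5–97.4%;
- intervals are about 11–37% wider than with prespecification.

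With no prognostic candidate, type I error and coverage stay near 5% and 95%, and power is about 0.4–4 points below baseline-only adjustment.

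**5. Mixed pools.** Six or ten candidates, two of them prognostic (correlation 0.3 or 0.4 each with the baseline-adjusted outcome), d>0.5, 3,000 trials per setting. The rule's power is 7–15 points below prespecifying those two, and 1–9 points below the same model without the selected covariates. Its type I error is 2.8–4.1%.

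**6. The beta-blocker stratum.** Assume half the patients take a beta-blocker and the arms are perfectly balanced on it (40,000 trials). The rule then always omits the stratum.

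| Residual variance explained | Correlation | Power, omitted | Power, included | Type I error, omitted |
|---|---|---|---|---|
| 10% | 0.5 | 88.5% | 90.5% | 3.9% |
| 10% | 0.8 | 81.9% | 84.6% | 3.9% |
| 30% | 0.5 | 90.4% | 95.7% | 2.1% |
| 30% | 0.8 | 84.0% | 92.2% | 2.0% |

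**The case against.** The strongest reply is that nothing decisive rests on these models. They are labelled exploratory, the primary test is the t-test on change, and the error under the rule is conservative: false positives are not inflated. All of this stands and limits the importance of the point.

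A reader might infer that the adjusted analysis is worse than no adjustment at all. The documents do not support that, because the baseline outcome is always a term. With ten candidates, two of them prognostic (correlation 0.4 each) and d>0.5, power for the t-test against the rule is 80% against 84% at baseline/follow-up correlation 0.5, 80% against 81% at 0.7, and 80% against 78% at 0.8. With four candidates, two prognostic, the rule did better than the t-test at every correlation from 0.3 to 0.8. It falls behind only when that correlation is high and most or all candidates are irrelevant.

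A reader might also infer that the candidates have no relation to outcome. The plan calls them confounders, which implies some relation. The gap is that they are unnamed and that entry still turns on imbalance.

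Nor is this regression the only safeguard. Randomization is stratified, and change scores are used because baseline balance in the outcome is not assumed. The same patients would also yield the same selected covariates for each objective; selection could differ mainly for HVPG, where some patients are excluded.

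Finally, Overall Patient Management has beta-blockers withheld for 3 days before each HVPG measurement, so the stratum may predict HVPG less strongly than the Randomization section suggests. That affects the size of the gain, not the fact that the rule would pass over the stratum.

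**Conclusion.** The point holds as a weakness of the exploratory regressions. Selection by observed imbalance makes the model depend on the allocation and tends to omit balanced prognostic covariates. Where some candidates are prognostic, it costs about 5 to 16 power points against prespecifying them, and its tests and intervals are conservative. Where none is, the intervals remain valid and the loss is about 0.4 to 4 points. These sizes rest on assumed numbers of candidates, prognostic strength, baseline/follow-up correlation and imbalance threshold; the direction does not depend on the exact values. It would be wrong to conclude that the primary analysis is compromised or that its stated 80% power changes.

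**What to change.** Delete the imbalance trigger. Before unblinding, fix the regression as treatment, baseline value of the outcome, the beta-blocker randomization stratum and at most one further covariate chosen on expected prognostic value, for example a baseline severity measure. With an intercept this is five parameters, leaving 30 − 5 = 25 residual degrees of freedom, or 24 − 5 = 19 at the 16:8 sample size considered in Power calculations. Report baseline imbalance descriptively only.

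The cost is a change of wording. The small downside is that a covariate off the list that turns out unequal by chance stays unadjusted; a sensitivity analysis that adds it, labelled as such, covers that case.

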The primary efficacy outcome will be to determine the effect of CBZ on hepatic ATZ load. This will be based on the number of hepatocytes with PAS+/diastase-resistant globules. Secondary measures will include the area of a liver section occupied by these globules. If there is enough tissue available for immunoblot analysis we will also use the steady state level of ATZ as a measure of hepatic ATZ load. For the secondary efficacy outcomes we will determine the effect of CBZ treatment on hepatic fibrosis on the basis of Sirius red staining and hydroxyproline concentration and whether CBZ treatment changes portal pressure as determined by HVPG. We will also determine if CBZ treatment reduces the MELD score by monitoring it at the beginning and end of the 12-month treatment period, including measuring at 7 follow-up visits while on active medication or placebo. The differences in the change in MELD score for subjects on active medication will be compared to that in subjects on placebo. Safety and tolerability will be investigated by close observation and routine laboratory testing of the 30 subjects.

A Preliminary Study of the Efficacy and Safety of Carbamazepine in Severe Liver Disease Due to Alpha-1 Antitrypsin Deficiency

STUDY POPULATION

Potential subjects for the study will be identified from the clinical practices of the pediatric and adult hepatology programs in the UPMC system and via outside referrals. The typical potentially eligible subject will have AT deficiency (ZZ and SZ phenotypes and low serum level) and clinical evidence of cirrhosis complicated by portal hypertension (e.g. splenomegaly or thrombocytopenia [platelet count <150,000 or a complication of portal hypertension (e.g. varices or ascites)]. HVPG measurement will be used as a screening procedure to determine if the potential study subject has documented significant portal hypertension (HVPG greater than or equal to 10 mm Hg or as indicated in inclusion criteria below). The research program will be advertised in relevant specialty journals and through the Alpha-1 Association. Interested individuals would need to be seen in the aforementioned clinical programs. Eligible subjects will be approached by one of the study investigators so that the study can be explained and inclusion/exclusion criteria can be reviewed.

SCREENING

Following a signed assent/consent, patients with AT deficiency will undergo a screening assessment to determine their eligibility for the interventional study.

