During therapy, study subjects will be seen on a regular basis to assess their clinical status and to obtain standard biochemical measures of liver and renal function, cell counts, etc. Visits will also include a full history and physical examination. Specific assessments and queries will be made for any signs or symptoms of liver disease. Child-Pugh (CP) score and MELD score will be calculated at each study visit. Other than blood collection during study visits, no additional invasive testing is proposed until the week 52b visit when a repeat liver biopsy and HVPg will be obtained. The procedure for the liver biopsy and HVPg will be identical to the procedure used in the screening visit. Data will be collected from procedures undertaken as part of clinical follow up (e.g. endoscopy reports, imaging studies, etc.).

If the study subject undergoes liver transplantation during the study period, samples will be obtained at the time of surgery to provide follow up data. If a subject dies during the study period and the family consents to an autopsy, samples of liver tissue will be obtained at autopsy to provide follow up data. In these cases, follow up HVPg measurements will not be available.

Potential for suicide attempts will be monitored with the Columbia Suicide Severity Rating Scale (C-SSRS) at study visits the week of enrollment through week 52a. It is a semi-structured, clinician-administered instrument to track severity of both suicidal behavior and ideation. This measure is reliable and valid and has been used in previous clinical trials (44, 45). Patients will be withdrawn from the trial if the C-SSRS identifies suicidal ideation or behavior and then the patient will then be referred for mental health evaluation and treatment.

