Study visits will be scheduled at weeks 4 (+/- 1 week), 8 (+/- 2 weeks), 18 (+/- 2 weeks), 36 (+/- 2 weeks), and 52a (+ 3 weeks) for a history and physical examination, assessment for depression and suicide behavior, biochemistry measures, and measurement of the blood level of the CBZ. Blood will also be collected at the time of enrollment and at week 52 visit for Fibrotest analysis. All female subjects of child-bearing age will undergo a urine pregnancy test on visit S2, enrollment, and at each follow up visit during the trial. The effect of CBZ treatment will also be assessed by a novel investigative test, a hepatic biomarker assay using samples that are obtained pre- and post-treatment as well as once during treatment. Study subjects may undergo MRI using Elastography within the first six months of study enrollment and at week 52 visit.

Additional visits may be scheduled, at the discretion of the Investigator, to ensure the safety and well-being of subjects. These will include a history, assessment for depression and suicide behavior, biochemistry measures, and measurement of the blood level of the CBZ. A physical exam may also be performed at the discretion of the investigator. Full list of assessments can be found on the schedule of events flow sheet.

A Preliminary Study of the Efficacy and Safety of Carbamazepine in Severe Liver Disease Due to Alpha-1 Antitrypsin Deficiency

Assessment of adherence:

Adherence will be assessed at each of the follow up visits by pill counts and patient medication diaries. Medications will only be available from the Investigational Drug Service (IDS), thus an accurate assessment of medication dispensed will be available. Subjects will be instructed to return unused medications at each visit. By pill count, medication adherence will be assessed. Adherence will be defined as intake of > 80% of the prescribed CBZ or placebo – persistent nonadherence to the study regimen may lead to discontinuation of the study for those subjects. For patients receiving CBZ, adherence will also be assessed by measuring trough CBZ levels at each visit. It is expected that the levels will be between 4 and 12 µg/ml. Standard deviations of sequential levels will also be used as a measure of adherence (46).

End of treatment assessment (week 52 visit + 1 wk):

Hepatic venous pressure gradient – see above

Liver biopsy – see above

Concomitant Medications:

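### MELD is recorded at every study visit, but its main analysis is an unadjusted two-point change with no rule for a missing final value

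*Combined protocol and SAP*

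**What the plan says.** Objective 5 asks whether treatment stabilises disease severity as measured by MELD. Under On-treatment assessments, "Child-Pugh (CP) score and MELD score will be calculated at each study visit". That section places the on-treatment visits at weeks 4, 8, 18, 36 and 52a, and Efforts to Ensure Adherence to the Protocol lists the same five time points. Study Design instead speaks of "monitoring it at the beginning and end of the 12-month treatment period, including measuring at 7 follow-up visits while on active medication or placebo".

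The Statistical considerations introduce MELD after Objective 3: "as an exploratory analysis we will assess whether CBZ treatment will lead to stabilization or improvement in disease severity". The method follows: "The analysis will compare treatment group differences in baseline to follow-up changes", and "Unpaired t-tests (or nonparametric equivalent if appropriate) will be the primary analysis". Regression models are offered as exploratory protection against covariate imbalance. As Objective 1 sets them out, they carry the imbalanced covariates "in addition to treatment group and baseline values of outcome measures".

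No slope, repeated-measures or mixed model is planned for MELD. The documents give no analysis population, no missing-data rule and no definition of the MELD follow-up value. They also do not say in general whether study visits continue after a subject stops treatment.

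**The concern.** HVPG and biopsy are two-point outcomes by necessity, because each needs an invasive procedure. MELD is not, but the plan applies the same two-point test to it. The plan also gives MELD a particular role: it may show clinical benefit if tissue heterogeneity hides an effect on ATZ load or fibrosis.

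Two things are at stake. The first is precision: an unadjusted change score is less efficient than a baseline-adjusted comparison, and the trial has only 20 and 10 subjects. The second is bias. A subject who deteriorates and stops early may have high MELD values at weeks 4 to 36 and none at week 52. Under a change-score t-test with no imputation, that subject contributes nothing. With ten placebo subjects, losing one or two of the worst from one arm could move the result.

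**Working it through.** **1. The plan's own figure.** Power calculations gives 80% power for 20:10, two-sided 5%, effect size 1.1. This is for the globule-count outcome; MELD has no power figure.
- Normal approximation: 1.1/√(1/20 + 1/10) − 1.96 = 2.84 − 1.96 = 0.88, so power is 81.1%.
- Noncentral t, 28 df: 78.3%.

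The stated figure reproduces. If subjects without a final value simply fell out of a test of that kind, power at 1.1 (noncentral t) would be 73.6% at 18:9, 68.0% at 16:8 and 61.6% at 14:7.

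**2. Assumptions for MELD.** The documents give no MELD standard deviation, between-visit correlation or dropout rate. I take a common variance (set to 1) and equal correlation r between visits, with r from 0.5 to 0.8 and up to 0.9 where stated.

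**3. Week-52 contrast, complete data.** Per-subject variance is 2(1 − r) for the change score and 1 − r² with baseline adjustment.

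| r | Change, 2(1 − r) | Adjusted, 1 − r² | Reduction |
|---|---|---|---|
| 0.5 | 1.00 | 0.75 | 25% |
| 0.7 | 0.60 | 0.51 | 15% |
| 0.8 | 0.40 | 0.36 | 10% |

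With complete data a longitudinal model gives the same week-52 variance as ANCOVA (ratio 1.00), so all of this gain comes from baseline adjustment. These are large-sample variances; with 30 subjects, estimating the adjustment costs a little.

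**4. Week-52 contrast with losses.** Dropout is assumed missing at random and spread evenly after weeks 4, 8, 18 and 36, with r from 0.5 to 0.9 and equal or exponentially decaying correlation. Using the intermediate visits then cuts variance by about 2-10% against complete-case ANCOVA at 10-30% loss. For an effect that gives the complete two-point test 80% power (normal approximation):

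| Loss | Two-point, complete cases | Longitudinal, week 52 |
|---|---|---|
| 0% | 80.0% | 82-90% |
| 10% | 75.7% | 79-87% |
| 20% | 70.7% | 76-84% |
| 30% | 65.0% | 72-80% |

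**5. Average over the five follow-ups.** Its adjusted variance is (1 + 4r)/5 − r², which is 0.35, 0.27 and 0.20 at r = 0.5, 0.7 and 0.8. It estimates a different quantity. If the effect grew linearly to week 52 (assumption), the mean effect would be (4 + 8 + 18 + 36 + 52)/5 ÷ 52 = 23.6/52 = 0.45 of the week-52 effect. Effect squared over variance, with the week-52 effect set to 1:

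| r | Average | Two-point change | Adjusted week 52 |
|---|---|---|---|
| 0.5 | 0.59 | 1.00 | 1.33 |
| 0.7 | 0.76 | 1.67 | 1.96 |
| 0.8 | 1.03 | 2.50 | 2.78 |

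The average beats the adjusted week-52 contrast only when its effect exceeds √(0.35/0.75) = 0.68, √(0.27/0.51) = 0.73 or √(0.20/0.36) = 0.75 of the week-52 effect.

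**6. Can the loss be informative?** The background section on liver disease names bilirubin, creatinine and INR as the MELD components. Indications to discontinue CBZ and the withdrawal list both include bilirubin above 7 mg/dl and an INR of 2.5 or more uncorrected by vitamin K. Two of the three components can therefore trigger stopping. Transplantation is also an indication to discontinue.

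**The case against.** The case for leaving the plan alone is reasonable. The MELD analysis is labelled exploratory, has no power calculation, and does not appear among the endpoints in the Summary. Comparing change between arms is a valid answer to the objective. Regression with baseline values is already planned, and with complete data that captures the whole week-52 gain. A mixed model assumes missing at random, so it does not settle death, transplantation or treatment failure. The plan itself warns that the sample limits how many terms a model can carry. All of this stands, and it keeps the point minor. It does not explain why the unadjusted test should be the main analysis, or why a missing final value has no rule.

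A reader might also infer that the plan excludes every subject without a final visit. The documents do not say so. Exclusion is only the default of a change-score t-test; the follow-up value is undefined, and On-treatment assessments treats tissue taken at transplantation as follow-up data, so an early or last available value is not ruled out.

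**Conclusion.** The point holds as a minor one. Repeated MELD values are collected and not analysed, the main comparison is unadjusted, and a missing final value has no rule although two MELD components are also stopping criteria. Under equal between-visit correlation, the week-52 gain is 25%, 15% or 10% in variance at r = 0.5, 0.7 or 0.8, all from baseline adjustment. The intermediate visits add about 2-10% when 10-30% of final values are lost at random. The documents give neither the correlation nor the loss rate, and whether any loss would favour one arm cannot be known from them.

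A reader might infer a much larger gain, 50-65% less variance, by setting the adjusted average over five visits against the two-point change (1 − 0.35/1.00 = 65%; 1 − 0.20/0.40 = 50%). That compares two different targets. It becomes power only if the effect is roughly constant over visits, and under a linearly growing effect the average carries less information than the planned test. The documents give no reason to expect a constant effect; under the scheduled weekly steps from 400 to 1200 mg/day, week 4 falls at about the end of dose escalation.

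**What to change.** - Make the main MELD analysis a longitudinal model on all scheduled visits, with treatment, visit, treatment-by-visit, baseline MELD and beta-blocker stratum (the randomisation stratum). Name the covariance structure and a simpler fallback: an unstructured matrix for five visits has 5 × 6/2 = 15 parameters, which is many for 30 subjects.
- Take the week-52 difference as the target. Report the average over follow-up as supportive only, and keep the planned t-test as a sensitivity analysis.
- Define the week-52 MELD value and state how values after transplantation, death or treatment failure are handled, with a sensitivity analysis that does not rely on missing at random.
- Reconcile the seven follow-up visits in Study Design with the five scheduled under On-treatment assessments. Also settle whether MELD is secondary, as its place in Study Design suggests, or exploratory, as the Statistical considerations say.

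The cost is analysis wording and a little more programming. No new data or visits are needed.

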The only available data come from studies we have carried out in mice. We found statistically significant differences between 18 treated and 11 placebo mice in the number of globule-containing hepatocytes after CBZ treatment. At the end of the study there were an average of 1088 (sd=260) globule-containing hepatocytes among control and 323 (sd=179) globule-containing hepatocytes among treated mice (14). Assuming that the average number of globule-containing hepatocytes at baseline was the same in the two groups of mice, then the group difference at follow-up (765 globule-containing hepatocytes) reflects the group difference in changes. Assuming equal standard deviation (sd) in the two groups, the effect size was 3.5. Then, for the proposed sample size (20 treated:10 controls) and a two-sided type I error of 5% there would be 80% power even if the effect is 1.1, about 1/3 of what was found in mice. This translates to being able to detect a drop in the treated group of 765 globule-containing hepatocytes compared to a drop in the controls of 514 (rather than 0).

For the second objective of fibrosis the only relevant data come from hepatic hydroxyproline concentrations in mice after CBZ treatment. There were statistically significant differences between the treated and placebo groups in hepatic hydroxyproline concentrations after CBZ treatment with values of 2.27 (sd=1.02) in 24 control mice and 1.21 (sd=0.70) in 25 CBZ-treated mice (14). Assuming that the hepatic hydroxyproline concentrations at baseline were the same in the two groups of mice, then the group difference at follow-up (1.06) reflects the group difference in changes. Assuming equal standard deviation (sd) in the two groups, the effect size was 1.2. Then, for the proposed sample size (20 treated:10 controls) and a two-sided type I error of 5% there would be 80% power even if the effect is 1.1, about 1/10 of what was found in mice. This translates to being able to detect a drop in the treated group of 1.06 compared to a drop in the controls of 0.106 (rather than 0).

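### The detectable differences for globules and hydroxyproline treat the SD of end-of-study mouse values as the SD of the change from baseline; the 80% power at about 1.1 SDs stands, but its translations rest on an unstated correlation

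*Combined protocol and SAP*

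**What the plan says.** Under Statistical considerations, Analysis, Objective 1 compares the arms "in the change from baseline to follow-up in the number of hepatocytes with PAS+/diastase-resistant globules using an unpaired t-test". Objective 2 compares "treatment group differences in baseline to follow-up changes in hepatic hydroxyproline concentration using an unpaired t-test". Both outcomes are therefore analysed as changes, and the Objective 1 text says this was chosen over a comparison of end-of-treatment values.

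The Power calculations section draws on mice for both outcomes. For globules it reports "statistically significant differences between 18 treated and 11 placebo mice" and continues: "At the end of the study there were an average of 1088 (sd=260) globule-containing hepatocytes among control and 323 (sd=179" in treated mice. It assumes equal baseline averages and concludes "then the group difference at follow-up (765 globule-containing hepatocytes) reflects the group difference in changes". Assuming equal SDs in the two groups, it then gives an effect size of 3.5. It states 80% power at an effect of 1.1, described as about a third of the mouse effect. This is translated into a treated-arm drop of 765 "compared to a drop in the controls of 514 (rather than 0").

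For hydroxyproline the values are 2.27 (SD 1.02) in 24 control mice and 1.21 (SD 0.70) in 25 treated mice, with the parallel step "then the group difference at follow-up (1.06) reflects the group difference in changes". The effect size is given as 1.2. The section again states 80% power at 1.1, here called about 1/10 of the mouse effect, and translates it into a drop of 1.06 against 0.106.

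**The concern.** An unpaired t-test on changes has the SD of the change in its denominator. Equal baseline averages let the follow-up mean difference stand for the difference in mean changes, but they do not make the SD of follow-up values equal to the SD of the change. The assumption of equal SDs concerns the two arms, not follow-up against change. For neither outcome does the section give a change SD, a baseline SD or a baseline/follow-up correlation.

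The absolute differences the trial is said to detect, and the margins claimed against the mouse effects, are therefore not derived for the named test. Those figures are what a reader would use to interpret a null result. The matter is sharpest for fibrosis, where the mouse effect (1.2) is barely above the detectable effect (1.1).

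**Working it through.** **Inputs** (all from Power calculations): 20 treated and 10 placebo; two-sided 5%; globule SDs 260 and 179, mean difference 1088 − 323 = 765; hydroxyproline SDs 1.02 and 0.70, mean difference 2.27 − 1.21 = 1.06.

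**1. Reproduce the stated figures.**
- Noncentral t with 28 df and noncentrality d × √(20 × 10/30): power is 78% at d = 1.1 and exactly 80% at d = 1.124. The stated 1.1 is a fair rounding.
- Root-mean-square SDs: globules √((260² + 179²)/2) = 223.2; hydroxyproline √((1.02² + 0.70²)/2) = 0.875.
- Effect sizes: 765/223.2 = 3.43 (stated 3.5); 1.06/0.875 = 1.21 (stated 1.2).
- Globule translation: 1.124 × 223.2 = 251, and 765 − 251 = 514, the printed figure. The end-of-study SD was therefore used as the SD of the change.
- Hydroxyproline translation: 1.124 × 0.875 = 0.983, and 1.06 − 0.983 = 0.077, not 0.106. The printed difference, 1.06 − 0.106 = 0.954, has 78% power with this SD. The figure 0.106 is exactly a tenth of 1.06, which matches the 1/10 wording. But 1.1/1.2 = 0.92, so the detectable effect is about 9/10 of the mouse effect.

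**2. Put in the SD of the change.** With equal baseline and follow-up SDs, SD of change = SD × √(2(1 − r)). This equals the end-of-study SD at r = 0.5, is larger below that and smaller above it. The documents do not give r, so the values below are assumptions.

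| r | √(2(1 − r)) | Globules: 80% detectable difference (cells) | Globules: power for 251 cells | Globules: power for 765 cells | Hydroxyproline: 80% detectable difference | Hydroxyproline: power for 1.06 |
|---|---|---|---|---|---|---|
| 0 | 1.414 | 355 | 51% | >99.9% | 1.391 | 57% |
| 0.25 | 1.225 | 307 | 63% | >99.9% | 1.204 | 69% |
| 0.5 | 1.000 | 251 | 80% | >99.9% | 0.983 | 86% |
| 0.75 | 0.707 | 177 | 98% | >99.9% | 0.695 | 99% |

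Each detectable difference is 1.124 × SD × √(2(1 − r)). Each power is the noncentral t power at the difference divided by SD × √(2(1 − r)). For example, 765 cells at r = 0 is 765/(223.2 × 1.414) = 2.42 SDs.

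**3. Threshold for fibrosis.** The full mouse effect reaches 80% power when 1.212/√(2(1 − r)) = 1.124, so r = 1 − (1.212/1.124)²/2 = 0.42.

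**4. Dependence on equal SDs.** In general the change SD is no larger than the follow-up SD when r is at least SD(baseline)/(2 × SD(follow-up)). If, as an assumption, both arms started with the control SD, the treated arm would need 260/(2 × 179) = 0.73 for globules and 1.02/(2 × 0.70) = 0.73 for hydroxyproline.

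**The case against.** The strongest reply is that the power statement is standardised. In SDs of the change, 20 against 10 gives 80% power at about 1.1 whatever r is. That is correct. A reader might infer from the mismatch that the stated 80% power is itself wrong, or holds only at r = 0.5. The documents do not support either reading: only the translations and mouse comparisons depend on r, and a higher r makes them conservative.

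A reader might also infer that r must be low, because the protocol allows that an effect may be missed "because of variability and heterogeneity within the liver" and cites sampling variability in its rationale for the placebo control. Those remarks bear on r but do not set it. Eligibility spans ages 14 to 80 and ZZ or SZ phenotypes, and wide spread between patients would raise r. The printed differences may be optimistic, about right or conservative.

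Nor are these figures the only basis for the sample size, since the section says resources limited it. The analysis text also concedes that only relatively large effects can be detected.

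Finally, extrapolating from mice to human biopsies may be a larger uncertainty than r, and the section says openly that only mouse data exist. This limits how precise any table can be. It does not justify printing differences computed for another variable's SD.

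**Conclusion.** The point holds for the translations. The Power calculations section uses the end-of-study SD as the SD of the change without saying so, and 514 reproduces exactly on that basis. The absolute differences and mouse comparisons are secured only if the change SD is no larger than the end-of-study SD, which means r of at least 0.5 under equal baseline and follow-up SDs.

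For the primary outcome the effect is confined to the claimed margin of about a third of the mouse effect, because the full mouse difference is safely powered even at r = 0. For fibrosis the margin is thin, and 80% power for the full mouse effect needs r of about 0.42 or more. The 0.106 and 1/10 figures are wrong in any case.

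A reader should not conclude that the trial is shown to be underpowered: r is unknown. These results rest on the mouse SDs carrying over to patients, all 30 patients contributing paired data, and equal SDs at both times.

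**What to change.** In Power calculations, for the first and second objectives:

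- State that 20:10 gives 80% power for a between-arm difference of 1.12 SDs of the change.
- Replace the 514 and 0.106 translations with a small table over r (for example 0.25, 0.5 and 0.75), stating the assumption of equal baseline and follow-up SDs.
- Correct the 1/10 wording: 1.1 is about 9/10 of the mouse hydroxyproline effect of 1.2.
- Say that the fibrosis comparison has 80% power for the full mouse effect only if r is about 0.42 or more.

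The cost is a few sentences and one table. Sample size, endpoints and tests do not change. The downside is a stated figure that may look less favourable, mainly for fibrosis.
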